6.2.1 Safety/Pregnancy-related policy

Safety Measures: To ensure that the participant does not have any underlying health conditions, such as significant liver or kidney disease, the study team will review medical records from the hospitalization.

Hypoglycemia: Subjects will be monitored with bedside glucose meters 4 times daily as per usual standard of care. Subjects may have additional monitoring if hypoglycemia is noted, or if the patient complains of symptoms of hypoglycemia, or at the request of the treating physician. Hypoglycemia is treated as per standard of care at Boston Medical Center, with 16 grams of glucose given orally, followed by a repeat BG in 15 minutes for patients able to eat. For patients

not able to eat, 12.5 grams of dextrose will be administered from a 50% dextrose solution IV, followed by a repeat BG in 15 minutes.

Pregnancy: A negative urine pregnancy test is required for all women of childbearing potential at screening. The sponsor-investigator will report to Novo Nordisk any pregnancy occurring during the trial period. Reporting of pregnancy by sponsor-investigator will occur within the same timelines described for reporting of Adverse Events. Pregnancy complications will be recorded as adverse event(s). If the infant has a congenital anomaly/birth defect this must be reported and followed up as a serious adverse event.

6.2.1.1 Storage and study Drug Accountability

Study insulins will be stored per institutional research standard procedures and in accordance with US product label instructions at the Investigational Pharmacy Service at BMC. Insulins used in the study will be administered as per usual standard of care by the hospital nursing staff and drug accountability will be performed by the study team and Investigational Pharmacy.

6.2.1.2. Adverse Events Definition and Reporting

Adverse Event: An Adverse Event (AE) is any undesirable medical event occurring to a subject in a clinical trial, whether or not related to the trial product(s). This includes events reported from the first trial related activity after the subject has signed the informed consent and until post treatment follow-up period as defined in the protocol, which in this study will be the last study visit. The following will not be recorded as AEs, if recorded as medical history/concomitant illness on the CRF at screening:

- Pre-planned procedure, unless the condition for which the procedure was planned has worsened from the first trial related activity after the subject has signed the informed consent
- Pre-existing conditions found as a result of screening procedures

Clinical Laboratory Adverse Event: A clinical laboratory AE is any clinical laboratory abnormality regarded as clinically significant i.e. an abnormality that suggests a disease and/or organ toxicity and is of a severity, which requires active management, (i.e. change of dose, discontinuation of trial product, more frequent follow-up or diagnostic investigation).

Serious Adverse Event (SAE): A serious AE is an experience that at any dose results in any of the following:

- Death
- A life-threatening* experience
- In-patient hospitalisation or prolongation of existing hospitalization
- A persistent or significant disability/incapacity
- A congenital anomaly/birth defect
- Important medical events that may not result in death, be life-threatening*, or require hospitalisation may be considered an SAE when, based upon appropriate medical judgement, they may jeopardise the subject and may require medical or surgical intervention to prevent one of the outcomes listed in this definition
- Suspicion of transmission of infectious agents

*The term life-threatening in the definition of SAE refers to an event in which the subject was at risk of death at the time of the event. It does not refer to an event which hypothetically might have caused death if it was more severe.

Unanticipated Problem: An unanticipated problem is defined as an event, experience or outcome that meets **all three** of the following criteria:

- is unexpected (in terms of nature, severity, or frequency) given (a) the research procedures that are described in the protocol-related documents (such as the IRB-approved research protocol and informed consent document); and (b) the characteristics of the subject population being studied; AND
- is related or possibly related to participation in the research (in this guidance document, possibly related means there is a reasonable possibility that the incident, experience, or outcome may have been caused by the procedures involved in the research); AND
- suggests that the research places subjects or others at a greater risk of harm (including physical, psychological, economic, or social harm) than was previously known or recognized.

Serious Adverse Drug Reaction (SADR): An adverse drug reaction (ADR) is an adverse event (AE) for which a causal relationship to the trial product is at least possible i.e. causal relationship is conceivable and cannot be dismissed. Serious adverse reaction (SAR): Adverse event which fulfils both the criteria for a Serious Adverse Event and the criteria for an Adverse Reaction.

Suspected Unexpected Serious Adverse Reaction (SUSAR): An SAE which is unexpected and regarded as possibly or probably related to the trial/study product by the investigator.

Medical Events of Special Interest (MESI): A MESI is (1) a medication error (e.g. wrong drug administration or wrong route of administration) or (2) a suspected transmission of an infectious agent via the product

Precautions/Overdosage: Include information concerning precautions and procedures to be observed in the event of overdose by any trial product provided during the study.

Non-Serious Adverse Event: A non-serious AE is any AE which does not fulfil the definition of an SAE.

Severity Assessment Definitions:

- Mild: Transient symptoms, no interference with the subject's daily activities
- Moderate: Marked symptoms, moderate interference with the subject's daily activities
- Severe: Considerable interference with the subject's daily activities, unacceptable

Relationship to study medication Assessment Definitions:

- Probable: Good reasons and sufficient documentation to assume a causal relationship
- Possible: A causal relationship is conceivable and cannot be dismissed
- Unlikely: The event is most likely related to an etiology other than the trial product

Outcome Categories and Definitions:

• Recovered: Fully recovered or by medical or surgical treatment the condition has returned to the level observed at the first trial related activity after the subject signed the informed consent

- Recovering: The condition is improving and the subject is expected to recover from the event. This term should only be used when the subject has completed the trial
- Recovered with sequelae: As a result of the AE, the subject suffered persistent and significant disability/incapacity (e.g. became blind, deaf, paralysed). Any AE recovered with sequelae should be rated as an SAE
- Not recovered
- Fatal
- Unknown

Collection, Recording and Reporting of Adverse Events: All events meeting the definition of an adverse event must be collected and reported from the first trial related activity after the subject has signed the informed consent and until the end of the posttreatment follow-up period as stated in the protocol, which will be the day of the last study visit.

At each contact with the participant, the investigator or study staff will seek information on adverse events by specific questioning and, as appropriate, by examination. Information on all adverse events should be recorded in the source document, and also in the appropriate adverse event form of the CRF. All clearly related signs, symptoms, and abnormal diagnostic procedures results should be recorded in the source document. All adverse events occurring during the study period must be recorded. The information reported to the sponsor will include at a minimum the study name, patient identification (subject number, initials, sex, age), event and diagnosis if available, trial drug, reporter, causality, and outcome.

Unanticpated Problems should be reported to the BUMC IRB within 7 days of the PI learning of event. Adverse Events that are not Unanticipated Problems should be submitted during the annual continuing review.

All SAEs, SUSARs, and SADRs need to be recorded and reported to Novo Nordisk within 24 hours of investigator's knowledge of the SAE. The investigator must submit any updated SAE data to Novo Nordisk within 24 hours of it being available.

Post-study Adverse Event: All unresolved adverse events should be followed by the study team until the events are resolved, the participant is lost to follow-up, or the adverse event is otherwise explained. In the rare circumstance that a subject has experienced an adverse event directly related to being in this study, which has not resolved by the time of discharge, the study team will contact the patient by telephone daily until the adverse event has resolved. We anticipate that the only adverse event related to the study that could persist by the time of discharge would be CGM related risks. Due to the nature of the study, no delayed toxicities or withdrawal effects are expected after a participant has discontinued participation in the study. Therefore, no collection of new safety information will be done after participant's discontinuation from the study.

6.3 Study Procedures

Subjects eligible for study recruitment will have the nature, purpose, and risks of the study explained to them by the Investigator or their designee. They will be provided with a written copy of the informed consent form (ICF) for the study and given sufficient time to consider the study's implications before deciding to participate. Subjects agreeing to participate in the study will sign the ICF and be given a duplicate copy before undergoing any screening procedures. A unique ID number will be issued at the time of consent by the study team.

- Informed consent must be obtained before any study related activity.
- All screening evaluations must be completed and reviewed to confirm that potential participants meet all eligibility criteria.
- The investigator or their designee will maintain a screening log to record details of all participants screened and to confirm eligibility or record reason for screen failure, as applicable.

6.3.1 Informed Consent

All eligible and willing subjects will be consented prior to any procedures being performed. Subjects will be given the opportunity prior to the consent process to read and review the consent form. During the informed consent process, a study staff member, who is also a physician, will review main areas of the study design, address all subject concerns, reinforce the study's commitment to the subject and reinforce the commitment needed from the subject to be in the study. Subjects will be allowed as much time as they need prior to signing the consent form. If the subject is limit- or non-reader, a "teach back" method will be used at consent to ensure the subject understand the study.

6.3.2 Screening

Pre-screening: Potentially eligible participants will be identified from the list of inpatients with diabetes in Epic. Patients who meet the preliminary study criteria (determined by completion of the Pre-Screen Form, Appendix 3 by the research staff) will be approached to consent for the trial.

Screening Visit: Participants will first be asked to give written, informed consent. A screening visit from the study team to the patient bedside will be completed to confirm subject eligibility. Assessments and procedures at the Screening Visit include:

- Informed consent will be obtained from the patient
- Medical history will be obtained from the hospital chart and will be reviewed with the patient
- Antihyperglycemic therapy prior to hospitalization will be obtained from the hospital chart and will be reviewed with the patient
- Medications currently being administered in the hospital (to review for exclusion criteria) will be obtained from the hospital chart
- Demographics (self-reported and obtained from hospital chart) will be reviewed with the patient
- Vitals and anthropometrics (height, weight, BMI) will be obtained from hospital chart
- Laboratory tests available in medical record (HbA1c and serum creatinine) will be reviewed
- Urine pregnancy test will be administered to women of child-bearing potential who have not had a pregnancy test in the current hospitalization.

6.3.3 Recruitment and Enrollment

Recruitment: Subjects will be recruited by reviewing the list of inpatients with diabetes from Epic. The study team will review the patient's sex, age, medical history, medications, ability to speak English or Spanish and BMI from Epic Systems Corporation (EPIC) medical records. Patients meeting the study criteria will be introduced to the study by a clinician who may also be an investigator. These patients will be screened in-person by the study team.

Enrollment: Participants are enrolled in the study when they have signed the ICF. Patients who enroll will receive \$25 dollars per day of participation, with a maximum of \$75 per subject. Payment will occur via ClinCard (a reloadable debit card), which subjects will receive after the consent process. After completion of participation, the study coordinator will add \$25 to the card for each day of participation up to a maximum of \$75. At the onset of the study, participants will be enrolled on 4 regular inpatient floors only (Menino building floors 6 East, 6 West, 7 East, 7 West), but this will be expanded to all other regular med-surg inpatient floors and stepdowns after the recruitment of 10 participants OR two months from study onset (whichever occurs first).

During the study: Please refer to section 5.1 General Design Description for a detailed review of what will happen once patients are recruited in the study.

6.3.4 End of Study and Follow-up

When participants have been in the study for three days the study will be completed. At study completion, participants with complete a Patient Reported Outcome (PRO) Questionnaire (Appendix 4). Patients may also be discontinued prior to 3 days if they withdraw consent, are transferred to a higher level of care, die during admission, are started on > 1 gram of acetaminophen and/or hydroxyurea by the primary medical/surgical team or are discharged from the hospital.

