3.2.2 CGM risks

The sensor insertion site will be inspected by the research staff daily. If subjects develop an infection at the sensor insertion site or an allergic reaction develops in response to the sensor, the adhesive, and other parts of the CGM, it will be removed and subjects can anticipate that their symptoms will clear up within one week. Subjects can also request removal if they develop pain, redness, swelling or minor bleeding at the CGM insertion site.

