4.3 Secondary Objectives

The secondary objectives of this study will assess whether our Fiasp® intervention is superior to NovoLog® in terms of postprandial glucose control (time spent in SG target range of 100-180 mg/dL in all of the 4 hour postprandial periods).

We will also assess glycemic control during other time periods during the study, and examine differences in hyperglycemia and hypoglycemia between groups. We will also analyze glucose variability and differences in insulin dosing between groups. All glycemic outcomes will be assessed using data obtained from CGM.

Secondary outcomes will include:

- 1. Percentage of time spent in the glycemic target range of 100-180 mg/dL (both inclusive) during the duration of the study.
- Percentage of time spent in the glycemic range of 70-140 mg/dL (both inclusive) in all of the 4 hour postprandial periods.
- 3. Percentage of time spent in nocturnal glycemic target range 100-180 mg/dL (both inclusive) during the nocturnal period (00.01 AM to 05:59 AM, both inclusive)

- Percentage of time spent with hypoglycemia (<70 mg/dL, <54 mg/dL, and <40 mg/dL respectively) in all of the 4 hour postprandial periods, in the nocturnal period (00.01 AM to 05:59 AM, both inclusive), and during the study.
- 5. Percentage of time spent with level 2 hyperglycemia (>240 mg/dL) in all of the 4 hour postprandial periods.
- 6. Percentage of time spent with level 1 hyperglycemia (181-239 mg/dL, both inclusive) in all of the 4 hour postprandial periods.
- 7. Mean SG glucose concentrations during the study.
- 8. Glucose variability as measured by standard deviation (SD) of glucose and coefficient of variation (CV).
- 9. Comparison of basal, prandial and correction insulin doses between the two groups.
- 10. Patient reported adverse effects from wearing a CGM and their perception of the experience of wearing a CGM while in the hospital.

5 – Study Design

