6.2 Assessments

The following assessments will be completed during the study:

Medical History: Study staff will obtain a prior history of diabetes and outpatient diabetes treatment medications. For women of non-childbearing potential, the reason should be documented.

Demographic/Medical information: Age, sex, BMI, vitals and reason for hospitalization will be obtained from the medical chart. Patients will be asked their self-identified race/ethnicity (white, black, Hispanic/Latino, Asian, or other). The most recent HbA1c if obtained during the index hospitalization or within 3 months prior to hospitalization will be collected from the medical chart. The serum creatinine at the time of randomization will be collected from the hospital record (note: serum creatinine is routinely obtained on all individuals admitted for inpatient care as part of the standard of care).

Blood Glucose Values/use of CGM: For insulin adjustment and treatment and monitoring of hypoglycemia, the standard hospital point of care meter will be used. At randomization a Dexcom G6 Pro CGM will be placed by the study team on the skin of the upper arm of the subject to collect blinded SG data during the study. The tiny sensor is under the skin and measures the interstitial glucose level, which is the glucose found in the fluid between the cells. The CGM device will be removed at the end of the study and the SG data from CGM will be used to assess glycemic outcomes.

If at any time the CGM becomes dislodged, a new device will be placed by the study team as soon as possible. If the patient must undergo a test during the study such as a CT scan or MRI where the CGM cannot be worn, the study team will remove the CGM prior to the test and place a new one as soon as possible immediately after the test.

Patient Reported Outcome (PRO) questionnaire: Study subjects will be asked to complete a questionnaire at the completion of the study (after sensor removal and before discharge). This questionnaire will assess the subject's perception of wearing a CGM device in the hospital and will also screen for adverse effects from wearing the CGM.

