Appendix 4. Patient Reported Outcome (PRO) Questionnaire

Instructions:

A Patient Reported Outcome (PRO) questionnaire is being included in this trial to obtain information about the acceptability of wearing a continuous glucose monitoring device while in the hospital.

When should the PRO questionnaire be administered?

At completion of the study. It takes approximately 5 minutes.

Before giving the PRO questionnaire to the subject

Fill in the header on each page

Giving the PRO questionnaire to the subject

-Explain that the questionnaire assesses the subject's perception of wearing a continuous glucose monitoring device in the hospital

-Explain that the subject should answer the questions him-/herself, without assistance from family, friends or medical staff

-Encourage the subject to answer every question to the best of his/her ability

-Ask the subject to select only one answer for each question

-Ask the subject to refrain from writing any extraneous comments in the questionnaire -Explain to the subject that the completed questionnaire will be reviewed for any written comments that may suggest issues with wearing the continuous glucose monitoring device

Completion of the PRO questionnaire

-Ensure that a staff member is accessible if questions arises

-If interpretive questions arise, ask the subject to read the question again and answer based on what he/she thinks the question means

-if the subject accidentally marks an incorrect response, ask him/her to strike it out with a single line and mark the correct response instead

After completion of the PRO questionnaire

-Collect the completed questionnaire from the subject

-Review them for potential adverse events and document the review on the designated signature sheet

-File the completed questionnaires in the trial file.

Questionnaire:

Trial ID:	Subject number:	Date: (DD/MMM/YYY):
Dear Study Participant,		
Please complete the quyou have reported any satisfied you are with v remain confidential. Th treated anonymously. monitoring device in th	estions on the following pages. The adverse effects with wearing the cor vearing it. Any adverse events will b ney will be compiled with the respon The data will be used to better unde e hospital.	study staff will review your answers to see if ntinuous glucose monitoring device, and how e reported. Otherwise, your responses ses from the other study participants and rstand the experience of wearing a glucose

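### The CGM questionnaire is timed only at study completion, so it is not assured for patients who leave early, and secondary outcome 10 can look too favourable

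*Combined protocol and SAP*

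**What the plan says.** Section 4.3 lists as the tenth secondary outcome: "Patient reported adverse effects from wearing a CGM and their perception of the experience of wearing a CGM while in the hospital". The instrument is the six-item questionnaire in Appendix 4.

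Its timing is given in three places:

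- Section 6.2: "Study subjects will be asked to complete a questionnaire at the completion of the study (after sensor removal and before discharge".
- Section 6.3.4: "At study completion, participants with complete a Patient Reported Outcome (PRO) Questionnaire (Appendix 4".
- Appendix 4: "At completion of the study. It takes approximately 5 minutes".

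Section 6.3.4 also says what completion is: "When participants have been in the study for three days the study will be completed". It then turns to earlier exits: "Patients may also be discontinued prior to 3 days if they withdraw consent, are transferred to a higher level of care, die during admission". That list goes on to excluded medication and hospital discharge.

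Section 3.2.2 provides for early removal of the sensor. For infection or an allergic reaction, "it will be removed and subjects can anticipate that their symptoms will clear up within one week". For milder problems, "Subjects can also request removal if they develop pain, redness, swelling or minor bleeding at the CGM insertion site". Section 6.3.5 separately allows the investigator to withdraw a participant because of an adverse event. None of these places mentions the questionnaire.

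**The concern.** A patient who leaves because the sensor hurt or irritated the skin has had exactly the experience that outcome 10 is meant to describe. If the questionnaire is given only to those who complete, whether an answer is missing can depend on what the answer would have been. The reported rates of discomfort and irritation would then tend to be too low, and the answers on preferring the sensor to fingersticks (items 5 and 6) too favourable.

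The analysis plan has nothing to offset this. Section 6.3.7.2 specifies t tests for time in glucose ranges and gives no method or denominator for the questionnaire. Section 6.3.8 is written for gaps in sensor data, so there is no rule for a missing questionnaire. Answers not collected in hospital are unlikely to be recovered later.

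**Working it through.** **1. Who is sure to be asked?**

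| Situation | What the protocol says | Questionnaire assured? |
|---|---|---|
| Reaches three days | Completion (6.3.4) | Yes |
| Sensor dislodged, or taken off for a scan | New sensor placed (6.2) | Yes, if the patient goes on to completion |
| Sensor removed for a reaction or on request | Removal only (3.2.2); not among the exits in 6.3.4; no replacement described | Not stated |
| Withdrawn for an adverse event, or withdraws consent | Exit (6.3.4, 6.3.5) | No |
| Discharged or transferred before three days | Discontinued (6.3.4) | No |

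The third row can be read either way. Section 5.1 expresses participation as hours of active sensor wear, which suggests that a patient without a sensor is finished. Section 6.3.4 does not list sensor removal as an exit, which suggests that the patient stays and is still due the questionnaire.

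**2. The plan's participant flow reproduces.** Inputs are from sections 5.1.1, 5.3.1 and 6.3.7.

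- Randomised per group: 80 / (1 − 0.10) = 88.9, so 89, or 178 in total.
- Consented: 178 / (1 − 0.15) = 209.4, so 210.
- Planned non-completers: 178 − 160 = 18, and 18/178 = 10.1%.

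The 18 is the allowance for every kind of dropout and early discharge. It is not a hard ceiling on missing questionnaires. Eligibility requires only 48 expected hours in hospital and section 5.1.1 plans 48 to 72 hours of wear, while section 6.3.4 classes discharge before three days as discontinuation.

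**3. Bounds for one sensor problem.** The documents give no problem rate, so this is an assumption: x of the 160 completers report it. If y of the 18 others had it too, the rate in all randomised is (x + y)/178.

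| Completers reporting it (assumed) | Reported rate | y = 0 | y = 18 |
|---|---|---|---|
| 8 of 160 | 5.0% | 8/178 = 4.5% | 26/178 = 14.6% |
| 16 of 160 | 10.0% | 16/178 = 9.0% | 34/178 = 19.1% |

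The lower bound lies below the reported rate, so the full range includes slight overstatement.

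**4. A narrower case.** Suppose k of the 18 left because of the sensor and all k had the problem, while the other 18 − k match the completers' rate p. The rate in all 178 is [160p + k + p(18 − k)]/178, and the understatement is k(1 − p)/178.

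| p (assumed) | k = 0 | k = 2 | k = 4 | k = 18 |
|---|---|---|---|---|
| 5% | 0 | 2 × 0.95/178 = 1.1 points | 4 × 0.95/178 = 2.1 points | 18 × 0.95/178 = 9.6 points |
| 10% | 0 | 2 × 0.90/178 = 1.0 points | 4 × 0.90/178 = 2.0 points | 18 × 0.90/178 = 9.1 points |

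The last column would need every dropout and every early discharge to be due to the sensor, which is not credible.

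**The case against.** A reader might infer that anyone whose sensor comes off early for a reaction is never asked, and that outcome 10 is therefore certain to be biased. The documents do not support that. Sensor removal is not a listed exit, and a patient who stays to day 3 without a sensor is still due the questionnaire. The section 6.2 timing, after removal and before discharge, would fit that patient. Section 5.1 also links successful completion to receiving the minimum of 4 meal doses, so some patients who go home before 72 hours may be treated as completers and be asked.

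A reader might also infer that sensor reactions would go unrecorded. They would not. Research staff inspect the site daily (3.2.2), ask about adverse events at each contact (6.2.1.2), and must document the reason for any withdrawal (6.3.5). This gives the adverse-effect half of the outcome a second source.

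Finally, both arms wear the same sensor, and the primary outcome does not use the questionnaire.

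All of this stands, and it limits the point without removing it. The section 6.2 wording permits the questionnaire after an early removal but does not require it. Staff records are not patient reports, nothing links them to outcome 10, and they do not supply the ease, graded discomfort and preference answers (items 1 to 3, 5 and 6).

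**Conclusion.** The point holds as a gap in a stated rule. The questionnaire is assured only at completion, so outcome 10 can be biased towards good tolerability if patients leave early because of the sensor. The direction is plausible, but the size cannot be determined from the documents. About 18 of 178 patients (10.1%) could lack a questionnaire on the plan's own allowance, with an unknown share related to the sensor. Under the stated assumptions (5% of completers with a problem, 2 to 4 sensor-related exits) the understatement is about 1 to 2 percentage points; it is zero if no exits are sensor-related and the non-completers resemble the completers. The effect falls on the overall description of tolerability, mainly the items with no other source. The primary outcome and the comparison of insulins are not materially affected. The change is worth making because it is cheap.

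**What to change.** In sections 6.2 and 6.3.4 and Appendix 4, time the questionnaire at final sensor removal or study discontinuation, whichever comes first and whatever the reason. Give it to every participant who wore a sensor, is able to answer and has not refused. This works whether or not removal for a reaction ends participation, but the protocol should state which applies, so that sections 3.2.2, 5.1 and 6.3.4 agree.

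Record the reason for each removal. Report outcome 10 with all who wore a sensor as the denominator, together with the number of missing questionnaires and the reasons. Show alongside it the removals for site reactions from the adverse event records.

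The cost is a wording change in three places plus a short reporting rule. At about 5 minutes each, 18 further questionnaires take about 18 × 5 = 90 minutes over the whole trial. Most would be given at a contact that already takes place, since section 5.1 has the sensor removed before discharge. Some answers will still be missing because of death, refusal or severe illness, which is why the count and reasons should be reported.
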